9.3.1.1. Transfusions

Transfusion data will be collected during the treatment and posttreatment periods throughout the study as specified in the Time and Event Schedules. Transfusion is monitored at each visit for imetelstat infusion (every 4-week cycle), at each disease evaluation visit, and at all unscheduled visits during treatment. During the posttreatment phase, transfusion data will be collected every 4 to 6 weeks until the first transfusion in follow-up. Enhanced operational monitoring will be implemented to seek transfusion information from other documented sources. Enhanced and continuous medical review will be implemented to identify any sudden but unsustained increase of Hb values and to query whether transfusion has occurred.

Data to be collected include the date of transfusion, number of units and type of blood products transfused and the pre-transfusion Hb and platelet count. Red blood cell transfusions may be administered based on Hb level, investigator's assessment of the subject's clinical signs and symptoms, and local clinical practice. As the volume of 1 unit of RBC transfusion may vary regionally, one unit is defined as the amount that is intended to raise Hb by approximately 1 g/dL

in an adult patient (ie, one standard pRBC unit or equivalent). The total number of RBC units required over rolling 8-week time periods will be calculated to identify subjects who achieve RBC TI or transfusion reduction.

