The distributions of OS, PFS, and time to progression to AML will be compared using a stratified log rank test for the ITT population. The Kaplan-Meier method will be used to estimate the distribution for each treatment. The treatment effect (hazard ratio) and its 2-sided 95% confidence intervals are to be estimated using a stratified Cox regression model with treatment as the sole explanatory variable. The reasons of censoring in time to progression to AML will be tabulated.

The time to 8-week and 24-week RBC TI will be summarized descriptively based on ITT 8-week and 24-week RBC TI responders, respectively. The Kaplan-Meier method will be used to estimate the distribution of duration of RBC TI based on ITT 8-week and 24-week RBC TI responders, respectively.

The amount and relative change in RBC transfusions will be summarized descriptively by treatment by time point.

Change from baseline in scores from QUALMS, FACT-An, and EQ-5D-5L will be summarized descriptively by treatment group. The PRO measure of interest and analysis methods (eg, responder analysis, longitudinal analysis with repeated measures) will be specified in the Statistical Analysis Plan.

A sequential gate-keeping procedure will be implemented to ensure that the overall type I error rate for the secondary endpoints is controlled. Details of selected secondary endpoints to be tested

and the testing procedure will be specified in the Statistical Analysis Plan.

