4.3 General Presentation Considerations

Continuous data will be summarized in terms of the mean, standard deviation (SD), median, minimum, maximum and number of observations, unless otherwise stated. Continuous data that are expected to be skewed will be presented in terms of the maximum, upper quartile, median, lower quartile, minimum and number of observations. The minimum and maximum will be reported to the same number of decimal places as the raw data recorded in the database. The mean, median, lower quartile and upper quartile will be reported to one more decimal place than the raw data recorded in the database. The SD will be reported to two more decimal places than the raw data recorded in the database. In general, the maximum number of decimal places reported shall be four for any summary statistic.

Categorical data will be summarized in terms of the number of subjects providing data at the relevant time point (n), frequency counts and percentages. Percentages will be presented to one decimal place and won't be presented for zero counts. Percentages will be calculated using n as the denominator.

Changes from baseline will be summarized using shift tables where appropriate.

P-values greater than or equal to 0.001, in general, will be presented to three decimal places. P-values less than 0.001 will be presented as "< 0.001". Confidence intervals (CI) will be presented to one more decimal place than the raw data.

In general, the analysis for Part 2 will be conducted by treatment group, for Part 1 by population type. The population type of Part 1 is specified as below:

- (1) All subjects: all subjects enrolled in Part 1;

- (2) Target population: the subjects with non-del(5q) MDS and without prior exposure to either hypomethylating agents (HMAs) or lenalidomide;
- (3) Other subjects: all Part 1 subjects excluding the subjects in the target population;

All report outputs will be produced using SAS[®] version 9.3 or a later version, and other software e.g. R as needed, in a secure and validated environment.

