4.9.1.1 Handling of Missing Data

No imputations for missing data will be made for the primary and secondary efficacy endpoints. The double-blind study design of Part 2 and the symmetric assessment schedule reduce the potential for systematic bias, but the treatment effect may be attenuated by missing transfusion data. In order to be considered transfusion independent, a subject must have completed continuous transfusion assessments throughout the qualifying observation period where his/her transfusion independence is determined. An apparent transfusion free period with one or more missing transfusion assessments will not be considered a qualifying 8-week or 24-week TI period. Subjects with no qualifying observation periods will be considered non-responders.

The number and percentage of subjects with missing data for the primary endpoint will also be summarized by major reason. In addition, a Kaplan-Meier plot of the time to study discontinuation will be provided.

A subject data listing will be provided showing all subjects with missing values for the primary endpoint. For these subjects, the listing will provide the observed data relating to the primary endpoint, important baseline characteristics, the recorded reason(s) for study discontinuation and the timing of study discontinuation.

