Progression free survival, defined as the time interval from Study Day 1 to the first date of disease progression or death from any cause, whichever occurs first. Subjects who received subsequent anti-cancer therapy prior to documented progression will be censored at the date of last evaluable response assessment or disease progression status conducted on or prior to the initiation of subsequent anti-cancer therapy. If subjects do not have any adequate post-baseline assessment and did not die, PFS will be censored at Study Day 1.

PFS will be computed as date of PFS event or censoring – Study Day 1+ 1.

Overall Survival (OS)

OS is defined as the interval from Study Day 1 to death from any cause. Survival time of living subjects will be censored on the last date a subject is known to be alive or lost to follow-up.

Time to progression to AML

Time to progression to AML is defined as the interval from Study Day 1 to the date of AML progression. Subjects who received subsequent anti-cancer therapy prior to documented progression will be censored at the date of last evaluable response assessment or disease progression status conducted on or prior to the initiation of subsequent anti-cancer therapy. If subjects do not have any adequate post-baseline assessment, time to progression to AML will be censored at Study Day 1.

Amount and relative change in RBC transfusions

Amount of RBC transfusions per 8-week (16-week) is defined as the total number of RBC transfusion units in a given 8-week (16-week) interval during study.

Relative change in RBC transfusions per 8-week = (amount of RBC transfusions per 8-week – prior RBC transfusion burden) / prior RBC transfusion burden multiply by 100%.

Relative change in RBC transfusions per 16-week = (amount of RBC transfusions per 16-week – total RBC transfusion units in 16 weeks prior to study entry) / total RBC transfusion burden in 16 weeks prior to study entry multiply by 100%.

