The starting date of an 8-week (16-week) interval must be between Study Day 1 and date of last dose of study drug + 30 days or End of Treatment Visit whichever occurs first, or Study Day 31 if randomized but not treated, and the ending date must be before the first transfusion in posttreatment follow-up or the first day of subsequent anti-cancer therapy whichever occurs first. Note that prior RBC transfusion burden is defined as the maximum number of RBC units transfused over an 8-week period during the 16 weeks prior to Cycle 1 Day 1 (C1D1) for subjects enrolled in Part 1 or the day of randomization for subjects enrolled in Part 2.

Rate of myeloid growth factor usage

Rate of myeloid growth factor usage is defined as the proportion of subjects who received any myeloid growth factors starting from Study Day 1. Duration of myeloid growth factor administered starting from Study Day 1 will also be summarized.

PRO measure of interest

See details in Section 4.11.6.

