The distribution of OS, PFS, and time to progression to AML will be compared using stratified log rank test for ITT analysis set. The Kaplan-Meier method will be used to estimate the

distribution for each treatment. The treatment effect (hazard ratio) and its two-sided 95% CIs are to be estimated using a stratified Cox regression model with treatment as the sole explanatory variable. The reasons for censoring of time to progression to AML will be tabulated.

For both Part 1 and 2, the amount and relative change in RBC transfusions will be summarized descriptively for each treatment group, and the relative and absolute change in transfusion amount in the best 8-week (16-week) interval (defined as an 8-week or 16-week interval where the subject had the fewest RBC transfusions on study) will be illustrated by waterfall plots. The distribution of duration from the start of the first 8-week interval that had ≥ 4 units of RBC transfusion reduction to the End of Treatment visit (or censored at the last dose day if still on treatment) will be estimated by the Kaplan-Meier method based on HI-E responders (transfusion reduction) for each treatment group.

Hemoglobin means, mean changes over time, and Hb rise (defined as the maximum Hb value in the longest transfusion free interval excluding values that were within 14 days after transfusion—the pretreatment Hb level) for subjects who achieved 8-week or 24-week RBC TI will be summarized for each treatment group. The longest transfusion free interval will be also illustrated by waterfall plots and swimmer-lane plots as appropriate.

Summary statistics (N, mean, SD, median, and range) and changes from baseline will be calculated for serum ferritin by scheduled visits for each treatment group. The usage of iron chelation therapy (ICT) will be summarized as well.

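### The transfusion-amount summaries keep an interval that runs past End of Treatment only if no posttreatment transfusion falls in it, so each arm's mean is biased downward

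*SAP*

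**What the plan says.** SAP 4.9.3.1 (Amount and relative change in RBC transfusions) defines the amount as the "total number of RBC transfusion units in a given 8-week (16-week) interval during study". Relative change compares it with the pre-study amount.

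Two rules decide which intervals are valid:

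- Start: the "starting date of an 8-week (16-week) interval must be between Study Day 1 and date of last dose of study drug + 30 days", or the End of Treatment visit if that is earlier (Study Day 31 for subjects randomized but not treated).
- End: "the ending date must be before the first transfusion in posttreatment follow-up or the first day of subsequent anti-cancer therapy whichever occurs first".

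Protocol 9.3.1.1 says that after treatment "transfusion data will be collected every 4 to 6 weeks until the first transfusion in follow-up".

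For reporting, SAP 4.9.3.2 says that "the amount and relative change in RBC transfusions will be summarized descriptively for each treatment group". Protocol 11.4 adds the time dimension: "The amount and relative change in RBC transfusions will be summarized descriptively by treatment by time point". SAP 4.3 gives the default statistics: "Continuous data will be summarized in terms of the mean, standard deviation (SD), median, minimum, maximum and number of observations". SAP 4.9.1.1 states: "No imputations for missing data will be made for the primary and secondary efficacy endpoints". No truncation at End of Treatment, rate per time observed, or sensitivity analysis is given for this endpoint.

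**The concern.** An interval of fixed length that starts by End of Treatment and ends on or after the first posttreatment transfusion must contain that transfusion. Two subjects with the same treatment dates are then handled differently. The one who needs blood in the weeks after stopping loses the whole interval, including the units given while on treatment. The one who needs none keeps it, with its low or zero count. The intervals that survive are selected for having few units.

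At stake is the description of transfusion burden over time in each arm, a listed secondary endpoint. If the mean is reported under this rule, both arms appear to need less blood than they did, most visibly around the times when many subjects stop treatment.

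**Working it through.** The documents give no figure for this endpoint, so there is none to reproduce. The check has four steps.

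**1. Closed form for one crossing interval.** Assumptions: episodes of 2 units arriving as a Poisson process at a constant rate before and after End of Treatment. Let B be units per 8 weeks, L the interval length in weeks, and s the weeks lying after End of Treatment. The episode rate is λ = B/(2×8) per week. The interval is kept with probability exp(−λs). A kept interval has mean B(L−s)/8, against a true B·L/8.

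- B = 8 (the Part 1 median baseline burden, Protocol 1.1.5), L = 8, s = 4: λ = 0.5. Kept: exp(−2) = 13.5%. Kept mean 8×4/8 = 4.0 against 8.0. Discarded intervals average (8 − 0.135×4)/(1 − 0.135) = 8.63.
- B = 8, L = 8, s = 2: kept exp(−1) = 36.8%, mean 6.0 against 8.0.
- B = 4, L = 8, s = 4: kept 36.8%, mean 2.0 against 4.0.
- B = 8, L = 16, s = 4: kept 13.5%, mean 12 against 16.

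**2. Dilution over all intervals.** Simulation with consecutive intervals from Study Day 1 and exponential time to End of Treatment with median 32 weeks (8 four-week cycles, the Part 1 median), unrelated to transfusion status. Assumed mixes at 0, 4 and 8 units per 8 weeks: 30/30/40% (imetelstat-like) and 7.5/30/62.5% (placebo-like). The 30% and 7.5% at zero are the design response rates.

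| Setting | Length | All intervals | SAP rule | Change |
|---|---|---|---|---|
| Imetelstat-like | 8 wk | 4.34 | 4.06 | −6% |
| Placebo-like | 8 wk | 6.17 | 5.98 | −3% |
| Everyone at 6 units | 8 wk | 5.98 | 5.88 | −2% |
| Imetelstat-like | 16 wk | 8.74 | 7.67 | −12% |
| Placebo-like | 16 wk | 12.47 | 11.92 | −4% |
| Everyone at 6 units | 16 wk | 11.95 | 11.79 | −1% |

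The mean falls in every row. In units, the fall is larger for 16 weeks in every setting. In percent, it is larger for 16 weeks in the two mixed settings but not when everyone has the same burden.

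**3. Between-arm difference.** From the table, the 8-week difference goes from 6.17 − 4.34 = 1.83 to 5.98 − 4.06 = 1.92 (+5%). The 16-week difference goes from 12.47 − 8.74 = 3.73 to 11.92 − 7.67 = 4.25 (+14%).

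Now let stopping differ by arm. Take 30% and 7.5% transfusion-free, the rest at 6 units per 8 weeks, and stopping among transfused subjects of 8% (imetelstat) and 25% (placebo) per 8 weeks. The 8-week means go from 4.07 to 3.98 and from 5.32 to 5.11. The difference goes from 1.25 to 1.13 (−10%). The 16-week difference is understated by about 9 to 13%. These stopping rates are assumptions, like the others; they show that the sign is not determined.

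**4. What the pooled rate recovers.** First 16-week interval, imetelstat-like: 30% at zero, 70% at 6 units per 8 weeks, stopping per 8 weeks 3% if transfusion-free and 12% or 20% if not. The true mean is 0.7×12 = 8.4. The SAP rule gives 7.8 or 7.3. For the pooled rate, mean days observed in 112 are (1 − exp(−112h))/h with h = −ln(1 − stopping rate)/56. That is 108.7 days for transfusion-free subjects and 98.8 or 90.3 for the others. Pooled units per 112 days:

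- 12% stopping: 12×0.7×98.8/(0.7×98.8 + 0.3×108.7) = 8.16
- 20% stopping: 12×0.7×90.3/(0.7×90.3 + 0.3×108.7) = 7.92

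The pooled rate is closer to 8.4 in both cases. What remains is a weighting by time on treatment, not selection on the counted outcome.

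**The case against.** The rule has a documented reason. Posttreatment transfusion data stop at the first transfusion, so a crossing interval that contains one has an incomplete count. That stands, and it means crossing intervals cannot be counted in full. It is a reason to cut every subject at the same point, not to discard only those who were transfused.

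The consequence is limited. The endpoint is descriptive and outside the gate-keeping and Hochberg sequence of SAP 4.9.1.3, so neither the primary analysis nor any type I error is touched. SAP 4.3 presents data expected to be skewed by median and quartiles, so the mean may not be the leading statistic. Selection on the outcome shifts the whole distribution, but the sizes shown here are for means. The documents also do not say whether intervals are consecutive or rolling, and the size depends on that.

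A reader might infer that the rule inflates the apparent benefit of imetelstat, because more zero-unit subjects remain in that arm. Step 3 shows why this does not follow: it holds under equal stopping among transfused subjects and reverses if transfused placebo subjects stop faster. The documents give no stopping rates by arm.

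A reader might also extend the point to the best-interval waterfall plots, or to HI-E by transfusion reduction, which has the same end rule. There, removing candidate intervals can only leave a subject's result unchanged or make it less favourable, so those results are not flattered.

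**Conclusion.** The concern holds for the amount and relative-change summaries. Inclusion depends on the outcome, and the arm means are biased downward. The direction follows from the text together with a transfusion need that does not fall on stopping; the size does not. In the illustrations the overall mean falls by 1 to 12%, and far more within crossing intervals alone (for example 4.39 to 1.50 units for 8 weeks in the imetelstat-like mix). These figures rest on assumed 2-unit episodes, a constant rate across End of Treatment, assumed burden mixes and stopping patterns, and consecutive intervals. Subjects still on treatment at the data cutoff are unaffected. The effect on the between-arm difference cannot be known from the documents. This should be corrected, but it does not threaten the trial's tested conclusions.

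**What to change.** For the amount and relative-change summaries in SAP 4.9.3.1:

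- Keep every interval that starts in the allowed window.
- For all subjects alike, count units and days from the interval's start to the earliest of its end, the End of Treatment visit (or last dose + 30 days), and the day before subsequent anti-cancer therapy.
- Per arm and time point, report total units divided by total days, scaled to 56 or 112 days. Do not average per-interval rates: 2 units in a one-day remnant would read as 112 units per 56 days.
- Base the relative change on the same pooled units and days, set against the pre-study amount of the same subjects.
- Remove the first posttreatment transfusion as a condition of validity.
- State whether intervals are consecutive or rolling.

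Keeping only intervals that end by End of Treatment is simpler, but it removes little of the bias when stopping depends on transfusion status.

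The cost is SAP wording and minor reprogramming; all data needed are already collected on treatment. The downside is that a rate replaces a fixed-window count, and subjects who stop early carry less weight (step 4). The summary should be labelled as an on-treatment rate.

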4.9.3.2 Analysis Methods

Part 1 (Phase 2):

The proportion of subjects with 24-week RBC TI, CR, PR, and hematologic improvement, and other binary endpoints, will be summarized with percentage along with its 95% 2-sided exact Clopper-Pearson CI. The time to 8-week RBC TI and time to 24-week RBC TI will be summarized descriptively based on 8-week and 24-week TI responder analysis set, respectively. The Kaplan-Meier method will be used to estimate the distribution of duration of RBC TI based on 8-week and 24-week TI responder analysis set, respectively. The distribution of OS, PFS, and time to progression to AML will be summarized using similar Kaplan-Meier methods.

Part 2 (Phase 3):

The 24-week RBC TI rates will be summarized with frequencies and percentages along with 2-sided 95% exact Clopper-Pearson CIs for the 2 treatment groups. Difference in TI and its 95% CI will be presented using Wilson Score method [1]. The comparison will be based on a stratified CMH test adjusting for the stratification factors at a two-sided significant level of 0.05.

Sensitivity analyses will be performed for Part 2 to evaluate the robustness of the 24-week RBC TI endpoint and includes:

- CMH test of 24-week RBC TI based on MITT analysis set in the case there are subjects who were dosed, but didn't receive any assigned treatment;
- CMH test of 24-week RBC TI based on per-protocol analysis set;

The time to 8-week and 24-week RBC TI will be summarized descriptively for the 2 treatment groups based on ITT 8-week and 24-week TI responder analysis set, respectively. The Kaplan-Meier method will be used to estimate the distribution of duration of RBC TI based on ITT 8-week and 24-week TI responder analysis set, respectively, and will be compared between two treatment groups using stratified log rank test based on ITT 8-week responder analysis set. The distribution of cumulative duration of RBC TI ≥ 8 weeks (sum of all durations of RBC TI ≥ 8 weeks) will be estimated by Kaplan-Meier based on ITT 8-week responder analysis set as well.

The proportion of subjects with hematologic improvement, CR, PR, or mCR per modified IWG 2006, and other binary endpoints will be evaluated using the same statistical methods as for the endpoint of 24-week RBC TI rates. The 8-week RBC TI rate in the first 24 weeks and 48 weeks (proportion of subjects who had RBC TI ≥ 8 weeks in the first 24/48 weeks) will be evaluated similarly.

The distribution of OS, PFS, and time to progression to AML will be compared using stratified log rank test for ITT analysis set. The Kaplan-Meier method will be used to estimate the

distribution for each treatment. The treatment effect (hazard ratio) and its two-sided 95% CIs are to be estimated using a stratified Cox regression model with treatment as the sole explanatory variable. The reasons for censoring of time to progression to AML will be tabulated.

For both Part 1 and 2, the amount and relative change in RBC transfusions will be summarized descriptively for each treatment group, and the relative and absolute change in transfusion amount in the best 8-week (16-week) interval (defined as an 8-week or 16-week interval where the subject had the fewest RBC transfusions on study) will be illustrated by waterfall plots. The distribution of duration from the start of the first 8-week interval that had ≥ 4 units of RBC transfusion reduction to the End of Treatment visit (or censored at the last dose day if still on treatment) will be estimated by the Kaplan-Meier method based on HI-E responders (transfusion reduction) for each treatment group.

Hemoglobin means, mean changes over time, and Hb rise (defined as the maximum Hb value in the longest transfusion free interval excluding values that were within 14 days after transfusion—the pretreatment Hb level) for subjects who achieved 8-week or 24-week RBC TI will be summarized for each treatment group. The longest transfusion free interval will be also illustrated by waterfall plots and swimmer-lane plots as appropriate.

Summary statistics (N, mean, SD, median, and range) and changes from baseline will be calculated for serum ferritin by scheduled visits for each treatment group. The usage of iron chelation therapy (ICT) will be summarized as well.

